4.1 Inclusion criteria

To be eligible for this trial patient must

1. Be capable of understanding the investigational nature of the study and all pertinent aspects of the study
2. Be capable of signing and providing written consent in accordance with institutional and federal guidelines
3. Have a histologically-confirmed diagnosis of breast cancer
4. Be willing and able to comply with scheduled visits, treatment plan
5. Age ≥ 21 years
6. Post-menopausal women with 1st event of ER+ early stage breast cancer (0-3)
7. Completed definitive therapy (surgery ± radiation)
8. Candidates for adjuvant AI therapy

4.2 Exclusion criteria

Patients who fulfill any of the following criteria will be excluded from the study

1. Have received adjuvant or neo-adjuvant chemotherapy

2. Prior endocrine therapy (AI or tamoxifen)
3. History of rheumatoid arthritis or other autoimmune arthritis
4. Daily NSAID use (except daily aspirin use)
5. Current use of daily corticosteroids or immunosuppressive therapies

4.3 Patient identification

Patients who have been consented and are undergoing study screening will be identified on study-related documentation and forms by their initials (first/middle and last name initials). All patients treated on this trial will be identified by their study initials and a unique study identification number. A unique study number will only be assigned to patients who meet the eligibility requirements and have completed the screening visit and are registered for treatment. The unique number will begin with the following prefix: AI. The prefix will be followed by the patient identification number beginning with # 001 in each cohort. These numbers will be issued to patients sequentially and no patient identification numbers will be re-assigned in the event that the subject withdraws from protocol treatment.

4.4 Study exit

Patients will exit the study upon completion of the last collection of blood for biomarkers and completing study questionnaires. Patients will not be followed further for purposes of this study.

5. Study Procedures

5.1 Pretreatment

Patients will be consented and evaluated for participation based on the following procedures before being registered and starting trial:

- History and physical exam (should be performed within 28 days of trial entry)
- Eligibility as determined by inclusion and exclusion criteria

5.2 Patient Registration

Patients must be registered prior to initiation of treatment. Patients will be registered through a Breast Team Clinical Research Coordinator (CRC) from 8:00 a.m. to 5:00 p.m., Mountain Standard Time, Monday through Friday, (excluding holidays)

Registration Guidelines

Before a subject participates in the trial, the investigator or delegate is responsible for obtaining written informed consent after adequate explanation of the aims, methods, anticipated benefits, subject responsibilities and potential hazards of the study and before any protocol-specific screening or study medications are administered. All patients must be registered before the start of treatment.

5.3 Research Blood Draw

Currently there are no blood based biomarkers evaluating AIMSS. We propose to prospectively collect blood for this pilot study for initial analysis of oxylipins.

Fasting blood will be drawn at the pre-determined time points (figure 1) and sent to [name] laboratory at the University of Arizona Cancer Center for further processing.

5.4 Self-reported questionnaires

The following questionnaires will be administered for the study to look for potential confounders like depression which can influence reporting of pain. The pain questionnaires will help us classify AIMSS in an objective way.

Pain Assessment. Breast Cancer Prevention Trial–Musculoskeletal Symptom (BCPT-MS) subscale and The Western Ontario and McMaster Osteoarthritis Index (WOMAC) have been validated as the most responsive tools for evaluating the development of AIMSS.⁶² These tools will be administered by the study nurse.

BCPT-MS: Individuals with a subscale score of ≥ 1.5 on the BCPT-MS are considered to have developed AIMSS, and it is expected that 50% of our sample will develop AIMSS.^{62,63} Our primary study endpoints will be correlated to three items on the BCPT-MS: general aches and pains, joint pain, and muscle stiffness.^{64,65} The BCPT-MS was derived from the original BCPT Symptom Check-list, a 18-item questionnaire validated in breast cancer survivors.⁶⁶ The subscale score consists of the mean of responses to three questions addressing general aches and pains, joint pain, and muscle stiffness(questions 8,9,10 of the attached subscale). Scores range from 0–4, with higher scores representing worse symptoms. Changes in the BCPT-MS subscale have been shown to be the most responsive to changes in AIMSS with 54% of women developing AIMSS within 6 months.⁶²

WOMAC: The WOMAC is a 24-item instrument developed to assess pain, stiffness, and physical function in participants with hip and/or knee osteoarthritis.⁶⁸ This instrument is well validated and has been modified from its original form, and used extensively to examine specific joint pain changes following treatment, including drug-based (NSAID) interventions for back pain, rheumatoid arthritis, and fibromyalgia.⁶⁹⁻⁷⁸ For our study, we will use the 5-point Likert format.

Depression Questionnaire. It has been reported that up to 50% of newly diagnosed breast cancer patients have symptoms of depression or anxiety⁷⁹ and perception of pain may be altered in individuals with symptoms of depression.⁸⁰ Therefore, we will also administer the Patient Health Questionnaire (PHQ)-9 questionnaire, which is a validated multipurpose tool used for screening, diagnosing, monitoring, and measuring severity of depression.⁸¹ Additionally, the PHQ-9 has been successfully used in breast cancer patients to evaluate psychometric properties.^{82,83}

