Adjuvant aromatase inhibitor (AI) therapy is the recommended first-line adjuvant treatment for postmenopausal women with estrogen receptor positive (ER+) breast cancer based on improved disease-free survival (DFS) compared to tamoxifen in randomized control trials. More recently extended adjuvant AI therapy (for 10 years) has been shown to improve DFS when compared to placebo in women who completed 5 years of standard AI therapy.^{1,2} However, AI therapy has been associated with significant, activity-limiting musculoskeletal symptoms including arthralgia, myalgia and joint stiffness or AI-induced musculoskeletal syndrome (AIMSS).³ AIs block estrogen synthesis and induce menopausal symptoms that are particularly severe in younger patients.^{4,5} Musculoskeletal complaints are among the most commonly reported and debilitating side effects of adjuvant AI therapy;⁶ findings that are supported by observations in aromatase knockout mice which exhibit increased pain responses.⁷ Among women with arthralgia syndromes at initiation of AI therapy, half report symptom exacerbation. Joint-related symptoms manifest early after initiation of AI therapy with worsening of symptoms up to 1 year post-initiation of AI.^{8,9} AIMSS impairs ability to perform activities of daily living as well as work-related tasks as the most commonly affected joints are hands, knees and hips.^{10,11} In a survey conducted by Breast Cancer Action, 27% of respondents reported that they had discontinued adjuvant AI use because of adverse effects (AE), with AIMSS being the leading AE.¹² In a cohort study in California, 61% of patients on AIs developed joint and/or bone pain resulting in discontinuation of therapy in 20% of patients.¹³ In a recent study, full adherence, defined as full duration and optimal schedule, was observed for only 49% of breast cancer (BC) patients prescribed any hormone therapy (HT) and was related to higher mortality in those who discontinued [Hazards Ratio (HR) = 1.26 (Confidence interval (CI) 1.09–1.46)] or were non-adherent to HT [HR = 1.49 (CI 1.23–1.81)].¹⁴ This study is concerning and consistent with clinical trial evidence from prior tamoxifen studies showing higher recurrence rates and worse outcomes with < 5 years or suboptimal HT use.^{15–17} Clearly, there is a need to maximize efficacy and improve tolerance to AIs. Approaches to study interventions that enhance both adherence and response rates for AIs are important research and clinical gaps that must be addressed to reduce death from breast cancer.^{18,19} **A critical first step is to identify those who are at risk of developing AIMSS by developing predictive biomarkers that will provide physicians opportunity for early intervention, thereby improving adherence to AIs. Currently there are no predictive biomarkers available to identify those at risk of developing AIMSS.**

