
Mechanisms of Aromatase Inhibitor-Associated Pain. The mechanism of AIMSS is not well understood and is grossly understudied. Based on observational data and animal data, it is likely that AIMSS is directly related, at least in part, to a) loss of the anti-nociceptive action of estradiol - resulting in greater sensitivity to stimuli and b) presence of underlying inflammation and the nociceptive activity or pain-inducing response of PGE₂. In aromatase-knockout mice, which lack endogenous estrogen production and serve as an animal model of AI therapy, estrogen deprivation results in a dominance of pro-nociceptive (pain) over anti-nociceptive response mechanisms following noxious stimuli such as formalin injection.²⁰ Results from experimental models to determine the role of estradiol in inflammation and specifically in cyclooxygenase (COX)-mediated PGE₂ are inconsistent and model dependent. Hunter *et al* demonstrated that ovariectomized rats exhibited greater sensitivity to a pain stimulus, as

measured by latency to paw withdrawal following an inflammatory insult.²¹ Serum levels of PGE₂ were increased in these rats, indicating an increase in inflammation. Pain sensitivity was reversed with estradiol replacement but serum PGE₂ levels did not change, indicating a separate mechanism for inflammatory response. The addition of a COX2 inhibitor increased latency to paw withdrawal compared to estradiol replacement alone, indicating a reduced pain response for these animals, and again indicating separate roles for inflammation and estradiol in pain response.²² Using this same model, ibuprofen (a non-steroidal anti-inflammatory drug, NSAID; a COX inhibitor) + estradiol replacement was shown to be more effective in reducing pain than either estradiol or ibuprofen alone.²² Collectively, these results indicate that the loss of estrogen alone does not increase pain by inducing PGE₂; but in the presence of PGE₂-mediated inflammation, estrogen deprivation increases sensitivity to inflammatory pain. **Therefore, if PGE₂ is elevated at baseline, this can predispose women to experience pain upon the depletion of estradiol with the addition of an AI.**

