In healthy women, joint and muscle pain worsen with age with greatest increases between 50 - 59 years.^{23,24} New onset of rheumatoid arthritis is also highest in the decade following menopause. Such observations, in combination with extensive experimental studies in animal models, have established estradiol as having both anti-inflammatory and anti-nociceptive properties.²⁴ Increased inflammation with aging, mediated by bradykinin and the pro-inflammatory prostaglandins (PGs), including PGE₂, has been mechanistically linked to hyperalgesia (increased sensitivity to painful stimuli) and allodynia (painful response to what would normally be an innocuous stimulus). Thus, inflammation and injury that stimulate PG release are thought to result in a heightened nociception and allodynia with the decline in estradiol levels with menopause.²⁵

Management of AIMSS in AI Patients. While all 3 third-generation AIs in routine clinical use cause different levels of estradiol suppression,²⁶ toxicity profiles are similar for all of them.²⁷⁻²⁹ Further, many studies show that there is no correlation with degree of estrogen depletion and pain in women on AI, regardless of AI type.^{30,31} Differences between agents in terms of quality of life (QOL) and tolerability are very important when selecting the optimal therapy for individual patients. Randomized clinical trials comparing tolerability and QOL between letrozole and anastrozole did not show any significant differences between the QOL scores. They did report that subjects who were intolerant to one AI were nonetheless able to tolerate another agent.^{32,33} Other studies have also demonstrated that switching AIs can result in improvements of AIMSS.^{33,34} This is a significant finding given that—despite AIs having similar toxicity profiles—AIMSS can sometimes be managed by switching AIs.

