Pain and oxylipins. How much pain interferes with daily activities such as walking ability was evaluated using the Brief Pain Inventory Short Form (BPI-SF). Oxylipin levels after a 3 month observation period were correlated with questionnaire items at the same time-point. **Table 2** presents the results from linear regression comparing how much pain interferes with walking ability and selected plasma oxylipin levels in 10 women stable on AI. PGE₂ levels were not correlated with how much pain interfered with walking ability. However, plasma levels of the LOX metabolite, 12-HETE, were significantly correlated. While not statistically significant, a similar pattern was observed across multiple LOX metabolites. This trend could still be observed in only 10 participants with overall low scores for how much pain interferes with walking ability (mean \pm SD; 2.48 \pm 2.45), which suggests a role for the LOX arm of the oxylipin pathway in the development of AIMSS. There was no correlation (positive or negative) with CYP450-derived metabolites and pain scores (data not shown).

While these results are promising and suggest that the LOX pathway may be related to AIMSS, samples from this clinical trial have several limitations. First, participants in this study were stable on AI for at least 6 months. Therefore, there is no true “baseline” to quantify oxylipins levels. Second, hand-specific symptoms, common in AIMSS, were not evaluated. Third, there is no BPI-SF score that specifically addresses AIMSS development. Fourth, while we have presented our preliminary data from the baseline (post-NSAID washout and 3 month observation period) only, women in this study initiate intervention with sulindac (a non-specific COX2 inhibitor). Thus, it is likely that the oxylipin cascade will be modulated by the intervention, and stored samples from this trial will not be appropriate to determine changes in oxylipins related to the natural history of AIMSS. Despite these limitations, these data demonstrate that oxylipins are quantifiable in the plasma of women currently taking an AI, and that they are present in a wide enough range of levels to relate to pain scores.

2. Study Objectives

Primary Objectives:

- To compare baseline oxylipin levels in women that do vs. those that do not develop AIMSS

Secondary Objectives:

- To correlate changes in levels of oxylipins with changes in pain scores through 6-month AI treatment.

3. Study design:

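### AIMSS is defined by an absolute BCPT-MS cut-off with no reference to the pre-treatment score, so the primary comparison can count pain that predates anastrozole as developed AIMSS

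*Combined protocol and SAP*

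**What the plan says.** The case rule is in section 5.4: "Individuals with a subscale score of ≥ 1.5 on the BCPT-MS are considered to have developed AIMSS". The subscale is the mean of items 8, 9 and 10, scored 0 to 4. With all three answered it moves in steps of one third, so 1.5 or more means 1.67 or more. The rule requires no pre-treatment score below the cut-off and no minimum rise, and it names no visit. The questionnaire in Appendix 12.1 asks how bothered the woman was over the past 4 weeks, not what caused the symptom.

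Sections 6 and 7 make the primary comparison one of baseline oxylipins (PGE2 and 12-HETE in section 7) between women who do and do not develop AIMSS, with 10 expected in each group. It is estimation only, and the estimated difference is meant to inform the size of a larger study. Change in BCPT-MS appears only in the secondary regression. The Study Calendar schedules the questionnaires before treatment and at 3 and 6 months, so the baseline score will exist.

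Section 4.2 excludes "History of rheumatoid arthritis or other autoimmune arthritis", daily NSAID use other than aspirin, and "Current use of daily corticosteroids or immunosuppressive therapies". It sets no limit on baseline BCPT-MS and does not exclude osteoarthritis or other joint pain. The Introduction recognises pain that is not due to the AI. It says that in healthy women "joint and muscle pain worsen with age with greatest increases between 50 - 59 years", and it reports: "Among women with arthralgia syndromes at initiation of AI therapy, half report symptom exacerbation".

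**The concern.** The study hypothesis is about prediction. The Introduction argues that if PGE2 is high at baseline, "this can predispose women to experience pain upon the depletion of estradiol with the addition of an AI". To examine that, the case group must hold women whose pain arose or worsened after the AI was started. An absolute cut-off also admits women who were already above it when the baseline blood was drawn. Two errors can follow:

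- If the oxylipin tracks current pain, a case/non-case difference appears even when the oxylipin predicts nothing.
- If women with pre-existing pain have oxylipin levels like those of the non-cases, a real difference shrinks.

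Either error enters the estimate that section 7 passes on to the design of the larger study. The groups could be redefined at analysis, but without a prespecified rule that choice would be made after about 20 women's data had been seen.

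**Working it through.** **The plan's own figure.** Section 7 gives a 95% CI width of 1.4 SD for 10 women per group. The t-based width for one mean is 2 × t(0.975, 9)/√10 = 2 × 2.262/3.162 = 1.43 SD, which agrees. For the difference, 10 v 10, it is 2 × t(0.975, 18) × √(1/10 + 1/10) = 2 × 2.101 × 0.447 = 1.88 SD, a half-width of 0.94 SD.

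**Simple count.** The share of women at 1.5 or more before treatment is not in the documents; assume 10%, 20% or 30%. Suppose all of them stay above the cut-off and half of the remainder cross it. Of 20 women the rule then labels 2 + 9 = 11, 4 + 8 = 12 or 6 + 7 = 13 as AIMSS. Of these, 18%, 33% or 46% had the score before treatment.

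**Model.** Not all such women stay above the cut-off, so I also used a bivariate normal model.

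- Baseline pain z0 and follow-up pain z1 have correlation ρ = 0.4 or 0.6 (assumed).
- A case is z1 above its median (the 50% of section 7).
- Prevalent women are the top 10%, 20% or 30% of z0.
- The oxylipin has correlation r with z0 and no other link to z1, so the true predictive effect is nil.

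The spurious difference in all women is r × 2ρ√(2/π), that is 0.638r (ρ = 0.4) or 0.957r (ρ = 0.6). Among baseline-negative women it is r times the figure in the table.

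| Prevalent | Share of cases, ρ = 0.4 / 0.6 | Difference in z0, baseline-negative, ρ = 0.4 / 0.6 | Fraction removed, ρ = 0.4 / 0.6 |
|---|---|---|---|
| 10% | 0.155 / 0.179 | 0.464 / 0.718 | 0.27 / 0.25 |
| 20% | 0.290 / 0.336 | 0.380 / 0.589 | 0.40 / 0.38 |
| 30% | 0.413 / 0.475 | 0.321 / 0.497 | 0.50 / 0.48 |

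The fraction removed is 1 minus the baseline-negative figure over the all-women figure, for example 1 − 0.464/0.638 = 0.27.

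**Values of r.** The Introduction's Table 2 (n = 10) gives R² = 0.44 for 12-HETE and 0.11 for PGE2, so r = 0.66 and 0.33. Fisher 95% limits, tanh(atanh r ± 1.96/√7), are 0.06 to 0.91 and −0.38 to 0.80.

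| r | Due to prevalent women (SD) | Left after removing them (SD) |
|---|---|---|
| 0.91 (upper limit, 12-HETE) | 0.16 to 0.42 | 0.29 to 0.65 |
| 0.66 (12-HETE) | 0.12 to 0.30 | 0.21 to 0.47 |
| 0.33 (PGE2) | 0.06 to 0.15 | 0.11 to 0.24 |
| 0.06 (lower limit, 12-HETE) | 0.01 to 0.03 | 0.02 to 0.04 |
| −0.38 (lower limit, PGE2) | −0.07 to −0.18 | −0.12 to −0.27 |

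The last column is general confounding by baseline pain, which a new-onset rule alone does not cure. With adjustment for the baseline score as well (assumed reliability 0.8, simulated), 0.07 to 0.14 SD remains at r = 0.66.

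**A rise rule used alone.** If cases are the top half of z1 − z0, the spurious difference is −2r√((1 − ρ)/2)√(2/π). At r = 0.66 this is −0.58 (ρ = 0.4) or −0.47 SD (ρ = 0.6): an artefact of the opposite sign.

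**The case against.** The best defence is that the word developed already means new onset. Section 5.4 introduces the tools as measuring development of AIMSS, notes that changes in the subscale are responsive, and a pre-treatment questionnaire is scheduled. On that reading the baseline condition is merely unwritten. I do not think this holds. The sentence defines developed by the absolute score, the remark on responsiveness describes the instrument, and no section turns either into a rule. Section 5.4 also says that the pain questionnaires together will help to classify AIMSS and that endpoints will be correlated with three BCPT-MS items, but it gives no WOMAC cut-off and no competing case rule. The cut-off is referenced to sources that I cannot see, so a baseline condition may exist there; the plan does not state one.

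Other points stand in part. Not every baseline-positive woman is a false case: the Introduction says that half of those with arthralgia at the start get worse, and a strict new-onset rule removes them from the case group. The section 4.2 exclusions may push baseline prevalence below the assumed range. The correlations come from 10 women already stable on AI, with a different pain item, and for PGE2 the text itself says that "levels were not correlated with how much pain interfered with walking ability". Half to three quarters of the illustrated bias is confounding that a new-onset rule alone would leave. These points limit what can be said about size, not the defect in the rule.

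**Conclusion.** The concern holds and should be fixed. Followed literally, section 5.4 counts stable pre-existing pain as developed AIMSS, and nothing in eligibility or in sections 6 and 7 prevents it. This conclusion rests on the text alone.

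The size is illustrative. It depends on an assumed baseline prevalence, an assumed pain correlation and a weak estimate of the oxylipin-pain correlation; it runs from negligible to about 0.4 SD, and its sign is not fixed. With a half-width of 0.94 SD for the difference, the pilot could not reveal a bias of that order. The consequence is limited because there is no formal test and all the needed data are collected.

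**What to change.** Amend sections 5.4 and 7 as follows, using data already scheduled:

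1. Define developed AIMSS as baseline BCPT-MS below 1.5 and 1.5 or more at any post-baseline assessment (3 months, 6 months, or the assessment at an early switch of AI). A prespecified rise from baseline is an alternative that keeps women who worsen, but only together with item 3.
2. Report women at 1.5 or more at baseline as a separate group, with their baseline oxylipins and change in BCPT-MS.
3. Give the PGE2 and 12-HETE differences adjusted for baseline BCPT-MS beside the unadjusted ones. State that adjustment may leave residual confounding, or remove part of a real effect that acts through baseline pain.
4. Keep the present absolute cut-off as a sensitivity analysis.
5. Restate the section 7 precision for the smaller groups.

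The cost is precision, and the loss of women who start high and truly worsen from the main case group. The width for the difference is 2 × t × √(1/a + 1/b):

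| Baseline prevalence (assumed) | Groups under the model | Width (SD) | Groups if 50% applies to baseline-negative women | Width (SD) |
|---|---|---|---|---|
| 0% | 10 v 10 | 1.88 | 10 v 10 | 1.88 |
| 10% | 8 v 10 | 2.01 | 9 v 9 | 2.00 |
| 20% | 7 v 9 | 2.16 | 8 v 8 | 2.14 |
| 30% | 6 v 8 or 5 v 9 | 2.35 or 2.43 | 7 v 7 | 2.33 |

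The case-group mean widens from 1.43 SD (n = 10) to 1.67 (n = 8), 1.85 (n = 7), 2.10 (n = 6) or 2.48 SD (n = 5). Under the model, the chance of fewer than five new-onset cases among 20 women is about 3-4%, 10-16% and 25-37% at 10%, 20% and 30% prevalence. Baseline adjustment changes the mean interval width by about −7% to +12%. Keeping 20 baseline-negative women would take 20/(1 − prevalence) = 23, 25 or 29 evaluable women. The planned 35 allow for 15 losses, so this is possible only if fewer are lost.
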